6. SPECIFIC AIMS

Aim 1: To compare the symptoms of PLWH+OSA vs. PLWH–OSA. This aim will allow us to test the hypothesis that fatigue is overexpressed in PLWH+OSA compared to PLWH–OSA, independent of known covariates. We will develop a multivariate model to predict fatigue based on clinical accessible data.

Aim 2: In those PLWH found to have OSA, we will:

a. Compare neurocognitive performance [psychomotor vigilance test (primary outcome), NIH Toolbox Cognition] in PLWH+OSA with low arousal threshold vs. those with a high arousal threshold. We hypothesize that stratified for similar disease severity, low arousal threshold induced OSA yields worse neurocognitive dysfunction compared to equal severity OSA with high arousal threshold.

b. Compare endothelial function (arterial tonometry) in PLWH+OSA with high loop gain (ventilatory instability with associated hypoxemia/hypercapnia) vs. those with low LG, to test the hypothesis that stratified for similar disease severity, LG-induced OSA yields worse endothelial function compared to equal severity OSA with low LG.

Aim 3: To test in PLWH+OSA whether 3 months of PAP treatment results in changes in OSA manifestations. This aim will allow us to test the hypothesis that endotype underlying OSA will be predictive of the specific clinical improvements seen in adherent users of PAP therapy. For example, those with high LG at baseline will have the greatest improvement in endothelial dysfunction with PAP therapy compared to other OSA patients with similar disease severity as measured by AHI.

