4. *Neurocognitive assessment:* Subjective assessment will be done using, Patient's Assessment of Own Function Inventory (PAOF) questionnaire. Objective assessment of brain function will be done using 10 minute psychomotor vigilance test (PVT). Neurocognitive assessment will be done using NIH Toolbox Cognition. This battery yields three composite scores: overall cognitive function, crystallized cognition and fluid cognition. The two tests of "crystallized cognition" are less sensitive to acquired brain dysfunction and reflect past learning experiences (Oral Reading Recognition and Picture Vocabulary). The five tests of "fluid cognition" assess multiple cognitive domains that are vulnerable to acquired brain dysfunction (i.e., Picture Sequence Memory Task = episodic memory, Dimensional Change Card Sort Task = executive function/flexibility, Pattern Comparison Task = processing speed, Flanker Inhibitory Control and Attention Task = executive function/inhibitory control, and List Sorting Task = working memory).

The NIH Toolbox battery has been nationally normed in a sample of 4,859 participants, English or Spanish speaking, ages 3-85 years, representative of the U.S. population based on gender, race/ethnicity, and socioeconomic status. Based on these data, demographically-corrected T-scores are available to adjust for age, gender, education, language and race/ethnicity.¹¹⁵ Additionally, this assessment tool is the result of an NIH initiative and is used in many studies, which allows for harmonization of findings. It can be completed in approximately 30 minutes.

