circadian rhythm, and we are supportive of such efforts in PLWH. Nevertheless, for the purposes of this application we believe we can use actigraphy coupled with examination by a Sleep Medicine expert to diagnose clinically relevant circadian disorders (such as advanced sleep phase disorder). The information from actigraphy will also be relevant in assessing activity levels and sleep/rest duration.

We anticipate that all of these procedures will take up to 4 hours. Per ACTRI clinic requirements, all subjects that are anticipated to remain at our study location over 2 hours will have to complete a COVID-19 swab. Our research group and/or the university will cover all charges associated with COVID-19 testing. Only subjects that are negative for SARS-CoV-2 virus can participate in the 4-hour visit.

Shortened in person Daytime Visit + Remote Daytime Visit #1

If COVID-19 is still a concern, we will split the daytime visit, so that it consists of a shortened in person daytime visit and remote daytime visit.

We will obtain consent during the in person daytime visit and complete the following study activities-- anthropomorphic assessment, lung function test, EndoPat, and neurocognitive assessment (NIH toolbox). An actigraphy watch will be given during the shortened daytime visit or mailed to the subject's home.

For the remote daytime visit, participants will be sent a personalized RedCap link in order to complete general health and sleep questionnaires. A researcher will be present on the phone to help troubleshoot and guide the remote daytime visit. The PI will also reach out to the subject to complete a structured interview over the phone or via Zoom in order to get a list of previous and current medications and substances they have used.

Overnight Visit #1. Due to the COVID-19 pandemic, the ACTRI clinic is requiring that subjects complete a COVID-19 swab within 72 hours of their overnight appointment. Only subjects that are negative for COVID-19 are allowed to complete this visit. Please note these requirements are subject to change. Subjects will arrive to the research sleep laboratory at approximately 8PM and undergo the following procedures:

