Additionally for subjects using PAP therapy for treatment of OSA, we will obtain a PAP download which will report therapeutic holding pressure, residual apnea-hypopnea index, as well as multiple parameters of adherence such as days of use, number of days >4 hours per night, etc. Mask type (nasal vs. oronasal, etc) will be recorded. The actiwatch will be returned to the investigators to assess the impact of PAP therapy on activity levels, pattern of activity and sleep duration.

We anticipate that Daytime Visit #2 will be 2 hours.

Shortened Daytime Visit and Remote Daytime Visit #2

As an alternative to having subjects come in for their final visit, subjects can complete the following activities remotely:

Subjects will be asked to complete all the questionnaires via a RedCap link. A researcher will remain on the phone in order to guide subjects and troubleshoot issues. The remaining study activities (anthropomorphic

assessment, lung function test, EndoPat, neurocognitive assessment) (NIH toolbox), 10 minute PVT, and blood sample) will have to be completed during a separate shorter daytime visit. An actigraphy watch may be mailed to the subject's home in order for data to be collected before their final daytime visit.

The total duration of the participant's involvement in the study is expected to be a total of 18 weeks.

Summary Information:

Clinical and research procedures: All of the study procedures are intended for research purposes only. However, it is anticipated that we will discover some previously undiagnosed sleep disorders, mostly obstructive sleep apnea. These subjects will be referred for a clinical sleep evaluation and treatment. Procedures carried out solely for research purposes: Overnight sleep studies (polysomnogram), pulmonary function testing, arterial tonometry (endoPAT), venipuncture, exhaled nitric oxide and carbon monoxide measurements

Devices: This study does not use any devices considered experimental or investigational. The sleep study equipment is FDA exempted. All FDA-regulated devices used in this study are approved for the proposed subject population and purpose. No significant risk devices are in use during this study.

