Sample Size Justification: Of the 120 PLWH studied in Aim 1, we believe that at least 60 will have OSA. We will split the cohort of those with OSA into high and low arousal threshold at the median value for the group. Although we will have multiple markers of cognitive function, our main outcome for Aim 2A for statistical purposes will be the psychomotor vigilance test (PVT). Prior work by Kribbs and colleagues reported a mean reciprocal reaction time of 3.9 seconds⁻¹ with a standard deviation of 0.5 (Ref 112). We believe that a change of 0.3 seconds⁻¹ represents a clinically important difference based on the effect size of CPAP observed with prior studies (Ref 123). Therefore, assuming a mean reciprocal reaction time of 3.9 seconds⁻¹ in those with low arousal threshold OSA and 4.2 seconds⁻¹ in those with high arousal threshold OSA, and a SD of 0.5 in both groups, we will have adequate power (beta >0.8) to detect a difference between the two groups (alpha = 0.05).

Statistical Analysis Plan: We will evaluate if there is a difference in PVT in OSA participants with low vs high AT using a two-sample t-test. As a sensitivity analysis, we will consider multiple regression models adjusting for additional covariates such as age, AHI, medications, mean sleep duration via actigraphy, and inflammation as assessed by CRP or IL-6 may be included in the modeling if significantly associated with outcome (p<0.10).

Aim 3 – Impact of OSA treatment on Sleep and Activity Phenotypes

To test in PLWH+OSA whether 3 months of PAP treatment results in changes in OSA manifestations. This aim will allow us to test the hypothesis that endotype underlying OSA will be predictive of the specific clinical improvements seen in adherent users of PAP therapy. For example, those with high LG at baseline will have the greatest improvement in endothelial dysfunction with PAP therapy compared to other OSA patients with similar disease severity as measured by AHI.

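### The split (COVID) Daytime Visit 1 does not schedule the 10-minute PVT, the Aim 2A main outcome, although the standard Visit 1 and the split Visit 2 both name it

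*Protocol*

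**What the plan says.** The PVT is the key measurement for Aim 2A. Protocol section 6 names the outcomes as "psychomotor vigilance test (primary outcome), NIH Toolbox Cognition", and the SAP (Aim 2, Sample Size Justification) says "our main outcome for Aim 2A for statistical purposes will be the psychomotor vigilance test (PVT").

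Protocol section 9 describes three daytime visits that bear on this point:

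- **Standard Daytime Visit 1, item 4.** Two tests, each with its own sentence: "Objective assessment of brain function will be done using 10 minute psychomotor vigilance test (PVT") and "Neurocognitive assessment will be done using NIH Toolbox Cognition".
- **Split Daytime Visit 1.** The in-person list is "anthropomorphic assessment, lung function test, EndoPat, and neurocognitive assessment (NIH toolbox"), with consent and an actigraph. For the remote part, "participants will be sent a personalized RedCap link in order to complete general health and sleep questionnaires", and there is an interview about medications and substances.
- **Split Daytime Visit 2.** Questionnaires are done remotely. The rest is done in person: "neurocognitive assessment) (NIH toolbox), 10 minute PVT, and blood sample) will have to be completed during a separate shorter daytime visit".

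The procedures for Overnight Visits 1 and 2 and for the home sleep test do not include the PVT.

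**The concern.** Aim 2A compares the PVT between participants with low and high arousal threshold. Arousal threshold is measured at Overnight Visit 2, which the protocol places before any clinical OSA treatment, so the matching PVT also has to be untreated. Once PAP has started, an untreated value cannot be obtained.

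Staff who work from the split Visit 1 lists are told to run the NIH Toolbox but are not told to run the PVT. If nobody notices before PAP begins, that participant drops out of the Aim 2A comparison. The SAP gives no rule for missing PVT values.

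**Working it through.** **Step 1. Where is the PVT scheduled?**

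| Contact (protocol section 9) | NIH Toolbox | PVT |
|---|---|---|
| Standard Daytime Visit 1 | named | named |
| Split Visit 1, in person | named | not named |
| Split Visit 1, remote | not named | not named |
| Overnight Visits 1 and 2 | not named | not named |
| Split Daytime Visit 2, in person | named | named |

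The two split visits use almost the same words for the Toolbox. The Visit 2 list then adds the PVT as a further item ("NIH toolbox), 10 minute PVT, and blood sample"); the Visit 1 list does not.

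**Step 2. Does another provision schedule it before PAP?**

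- *Make-up sentence after the EndoPAT description (Visit 1, item 5).* It allows procedures to be done just before the sleep study or at an extra visit. It sits under the cardiovascular item, it is unclear which procedures it covers, and its trigger is lack of time or equipment, not use of the split route.
- *Supplemental Daytime Visit.* It is headed optional and applies only if 12 weeks pass between the first visit and the start of PAP. It repeats the Visit 1 measurements without saying which version of Visit 1.
- *Payment for an additional daytime visit (section 20).* It funds a make-up but does not require one.
- *Overnight Visit 2.* It takes place in the laboratory and before treatment, so the test could be done there, but it is not listed.

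Recovery is therefore possible, but nothing on this route schedules it.

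**Step 3. What would a loss cost?**

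Inputs from the SAP, Aim 2: difference 4.2 − 3.9 = 0.3 per second; SD 0.5 in both groups; 60 participants with OSA, split at the median into 30 and 30; alpha 0.05. The SAP does not state sidedness for this test; two-sided is used here, as the SAP does for Aim 1.

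Standardised difference: d = 0.3 / 0.5 = 0.6. For n per group, the noncentrality is d × √(n/2) with 2n − 2 degrees of freedom, and power is read from the noncentral t distribution. Losses are taken as equal in the two groups.

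| PVT values lost (assumed) | Total n | n per group | Noncentrality | Exact power |
|---|---|---|---|---|
| 0% | 60 | 30 | 0.6 × √15 = 2.32 | 0.63 |
| 10% | 54 | 27 | 0.6 × √13.5 = 2.20 | 0.58 |
| 25% | 45 | 22.5 | 0.6 × √11.25 = 2.01 | 0.50 |

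**Step 4. The SAP's own figure.** The SAP states power above 0.8 (written as beta). It does not reproduce: complete data give 0.63 two-sided, or 0.74 one-sided. That shortfall of about 0.17 is there before any PVT is lost and belongs to the sample-size justification, not to this point. The effect of the omission is only the fall from 0.63: 0.05 at 10% lost and 0.13 at 25% lost (0.63 − 0.58 and 0.63 − 0.50).

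**The case against.** The best counter-reading is that nothing was dropped. Neurocognitive assessment is the heading of Visit 1 item 4, which contains the PVT as well as the Toolbox. The split list looks like shorthand for the Visit 1 items, and the protocol speaks of splitting the visit, not shortening its content. The split Visit 2 list is also loosely drafted: its brackets do not match, and it includes lung function testing, which the standard Visit 2 text excludes. It is thin evidence of careful itemisation. Since Visit 2 repeats Visit 1 measurements, the authors probably took a baseline PVT for granted.

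This makes a drafting slip likely, but it does not put the PVT on the list. The parenthesis ties the phrase to the Toolbox, as the item 4 text also does, and the aims treat the two tests as distinct.

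Three stronger conclusions that a reader might draw are not supported:

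- *That everyone on the split route would lack a baseline PVT.* The make-up routes and the pre-treatment laboratory night could each supply one, and the documents do not show how often they would.
- *That a planned pre-to-post PVT analysis is lost.* The SAP's Aim 3 plan names a paired test for EndoPAT only.
- *That the omission explains why Aim 2A falls short of its stated power.* The shortfall exists with complete data.

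**Conclusion.** The point stands as a gap in scheduling. On the split route, the protocol as written schedules no baseline value of the Aim 2A main outcome, and no other provision guarantees one before PAP. Whether data are lost depends on how sites read the list and whether make-ups are done.

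The size cannot be fixed from the documents, because the share of participants on the split route is not given and the route itself is conditional on COVID-19 remaining a concern. The power figures of 0.58 and 0.50 assume losses of 10% and 25%, spread evenly over the two arousal-threshold groups, with no make-up. The gap in the visit lists does not depend on any power figure. The change is worth making because a missed untreated PVT cannot be recovered after PAP starts and the correction costs very little.

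**What to change.** In protocol section 9, add the 10-minute PVT by name to the in-person list of the shortened Daytime Visit 1, as the shortened Daytime Visit 2 already does. Add one sentence saying that a baseline PVT missed at Visit 1 is made up at the latest at Overnight Visit 2, which is already in the laboratory and before OSA treatment. That sentence should place the test on arrival, before airway pressure is applied for the night, and have its time of day recorded, because an evening make-up differs from a daytime test.

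A general instruction to test before PAP adds little at Visit 1, which precedes the diagnostic sleep study; the deadline matters for make-ups.

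The cost is two short edits and about 10 more minutes in person at a visit the participant already attends. If sites already run the PVT at this visit, the edit simply brings the protocol into line with practice.

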10. HUMAN SUBJECTS

People living with HIV (n=120) will be recruited into the study to undergo a standard sleep study (polysomnogram, PSG), a research sleep study, and PAP trial.

Inclusion Criteria:

- Ages 18-65 years old
- BMI 20 – 35 kg/m²
- Physician diagnosis of HIV and viral suppression

Exclusion Criteria:

- Pregnancy

- Inability to complete study procedures, such as questionnaires that are only available/validated in English.
- Already on effective therapy and adherent to treatment for OSA
- Other known untreated sleep fragmenting disorder, such as periodic limb movement disorder, or narcolepsy

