9. RESEARCH DESIGN AND METHODS

Under each visit subsection, we have added alternatives for researchers to consider in order to maintain social distancing and perform study activities remotely due to COVID-19. After written informed consent has been obtained, the following procedures will be undertaken:

Daytime Visit 1 (Aim #1)

1. *Anthropomorphic assessment:* Baseline demographics and health status (medical problems, medications, allergies, social history) will be obtained. A basic exam, including height, weight, neck circumference, hip, and waist circumference, blood pressure, and oxygen saturation will be obtained.
2. *Lung Function Assessment using spirometry:* As per American Thoracic Society criteria. In brief, subjects will blow into a pneumotachogram via a mouthpiece with a nose clip in place from full inhalation to complete exhalation.
3. *Questionnaires:* Standard sleep related questionnaires will be used, including the Epworth Sleepiness Scale, Pittsburgh Sleep Quality Index, and Insomnia Severity Index (ISI). In addition subjective assessment of fatigue, depression, quality of life questionnaires, pain, and alcohol consumption will be

used including Functional Assessment of Chronic Illness Therapy Fatigue Scale (FACIT-F), Beck Depression Index-II, SF-36 Item Health Survey (SF-36), Brief Pain Inventory (Short Form), PROMIS pain intensity, PROMIS pain interference, Alcohol Use Disorders Identification Test (AUDIT), and Alcohol Dependence Scale (ADS). Subjects will also be given the FRAM body morphology questionnaire.

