If subjects are not found to have OSA, they will not continue with the study.

(End of Aim #1)

Aims #2 and #3

Subjects found to have OSA (with AHI >5 events/hour) will be referred for clinical evaluation (by a sleep physician not involved in the study) and treatment, and will also return for overnight visit #2, and continue to be followed with weekly phone calls and a repeat assessment 3 months after starting OSA treatment.

Overnight Visit #2 (Aim #2) Measurement of Endotypic Traits

This visit will be scheduled to occur within 1 month of visit 1, and will be prior to any clinical OSA treatment. Subjects will come to the sleep research laboratory about 2-3 hours before their usual bedtime. They will undergo polysomnography, as described above, without the physiological CPAP testing procedure. To review, the subject will have EEG, EMG, EOG, and ECG electrodes, an adhesive body position sensor placed in standard locations. Pulse oximetry sensor will be attached either to a finger or ear lobe and secured by tape. The following parameters will be measured during sleep: electroencephalogram, eye movement, electrocardiogram, electromyogram, leg movement, snoring sounds, nasal pressure, and nasal-oral air flow by thermistor, respiratory effort and body position by piezo-electric bands of the thorax and abdomen or magnetometers, position sensors, and pulse oximetry. This equipment is standard for diagnostic polysomnography and should not be uncomfortable.

Additional equipment for the physiological sleep study will also be applied to the subject, as follows:

A thin esophageal catheter (6-8 french) with an electrode array to measure diaphragm electromyography will be placed via the nares. Prior to the cannula placement the subject will receive 2 sprays of a nasal decongestant (0.05% oxymetazoline hydrochloride), followed by 4% lidocaine topical spray for local anesthesia. The catheter will be confirmed to be in the proper position by examining the signal, then taped to the nose (and later secured to the CPAP mask). The esophageal catheter placement may be omitted by subject or investigator request; in this case subjects can still remain in the study.

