20. COMPENSATION FOR PARTICIPATION

Subjects will be compensated after completing each portion of the study, as outlined below:

- Daytime Visit 1 (Aim 1): \$50
- Overnight Visit 1 (Aim 1): Routine Polysomnography: \$100
- Actiwatch returned (Aim 1): \$50
- Overnight Visit 2 (Aim 2): Research Polysomnogram: \$100
- Weekly Phone calls (Aim 3): Subject will be compensated for \$20 for answering each weekly follow-up call for 12 weeks, in total of \$240.
- Daytime Visit 2 (Aim 3): Day Testing \$50
- Actiwatch Returned (Aim #3): \$50
- If a separate visit needs to be scheduled for the fasting morning blood sample: \$20 for each visit
- If an additional daytime visit is needed for data collection: \$50
- If data is inconclusive and an additional polysomnogram night is required, they will be paid \$100.

Subjects will make up to a total of \$-660.00 for completion of the all study aims, unless additional data needs to be collected.

If subjects only complete Aim 1, compensation will be \$200.00.

If subjects only complete Aim 1 and Aim 2, compensation will be \$300.00.

Parking will be available free of charge and participants will also be reimbursed for minor out of pocket expenses including meal vouchers, public transportation or taxi vouchers. If the subject terminates the study early, they will receive an amount based on the visits that have been completed. If any of the visits are missed, the subject will not be compensated for those visits.

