26. IMPACT ON STAFF

This study is outside of any clinical care and thus will not impact any staff outside the research personnel. It is anticipated that we will diagnose 60 subjects with sleep disorders that require clinical evaluation over 4 years. This volume of patients can easily be handled by the UCSD Sleep Medicine clinic.

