Obstructive Sleep Apnea Endotypes and Impact on Phenotypes of People Living With
HIV

Statistical Analysis Plan

NCT03575143

October 5, 2018

Statistical Considerations:

Results will be reported as point estimates (odds ratios or mean differences across groups, as appropriate) and interval estimates (95% confidence intervals). All tests of significance for the secondary outcomes will be 2-sided and Bonferroni adjustments will be made for multiple comparisons as appropriate. A p-value of 0.05 will be considered statistically significant. Statistical analysis will be conducted using the statistical software R 3.3.3. (www.rproject.org). Demographic and baseline characteristics will be compared among the cases and controls using Fisher's exact test for categorical variables, and a two-sample t-test for continuous variables. Appropriate non-parametric alternatives will be considered, if parametric assumptions fail.

Aim 1 – Sleep and Activity Phenotyping

To compare the symptoms of PLWH+OSA vs. PLWH–OSA. This aim will allow us to test the hypothesis that fatigue is overexpressed in PLWH+OSA compared to PLWH–OSA, independent of known covariates.

Sample Size Justification: The study is expected to enroll 120 evaluable HIV subjects, not known to have OSA, or not on treatment for OSA, and not known to have any other sleep disorder (such as narcolepsy) other than symptoms of insomnia. Based on the literature cited above, we expect to find a 50% prevalence of OSA (defined as an AHI >5/hour using 4% criteria) such that 60 subjects will have OSA and 60 will not. FACIT-F scores in HIV have been reported by two groups with remarkably similar means and standard deviations (Ref 64, 108). The presence of witnessed apneas was associated with a 6.5 reduction in FACIT score (with 3 points considered clinically meaningful, lower scores are associated with worse fatigue). Therefore, assuming a mean FACIT-F score of 36 in those without OSA and 30 in those with OSA, and a standard deviation of 12 in both groups, we will have approximately 80% statistical power to detect a difference between the two groups. Power is based on a two-sided, two-sample t-test, assuming alpha is set to 0.05. To account for 10% attrition, we will enroll 134 subjects to achieve 120 evaluable subjects.

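### Protocol section 10 gives 120 as the number recruited, while the SAP enrols 134 to obtain 120 evaluable; section 10 should carry the SAP's attrition allowance

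*Protocol*

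**What the plan says.** Protocol section 10 gives one number, 120, attached to recruitment: "HIV (n=120) will be recruited into the study to undergo a standard sleep study (polysomnogram, PSG), a research sleep study, and PAP trial". Neither that section nor the rest of the protocol text available for review gives an attrition rate, an evaluable number or the figure 134.

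The SAP (Aim 1, Sample Size Justification) treats 120 as the number of evaluable participants, split 60 with OSA and 60 without on an assumed prevalence of 50%. It then adds the allowance for 10% attrition: "we will enroll 134 subjects to achieve 120 evaluable subjects".

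Three other places bear on how 120 should be read:

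- SAP, Aim 2, Sample Size Justification: "Of the 120 PLWH studied in Aim 1, we believe that at least 60 will have OSA".
- Protocol section 26 (Impact on Staff): "It is anticipated that we will diagnose 60 subjects with sleep disorders that require clinical evaluation over 4 years".
- Protocol section 9, at the end of Aim 1: "If subjects are not found to have OSA, they will not continue with the study".

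**The concern.** The same number stands for intake in one document and for what remains after attrition in the other. Section 10 is where study staff or an ethics reviewer would look for the number of participants, and a reader of the protocol alone would not learn that 14 more are planned.

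Those 14 are the whole attrition allowance. If recruitment stopped at 120 and attrition ran at the SAP's rate, the Aim 1 comparison of FACIT-F scores would fall short of the 120 evaluable participants on which its power rests. The OSA group that Aims 2 and 3 draw on would shrink in proportion. The SAP has no spare margin to absorb this.

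**Working it through.** **Inputs.** All are from the SAP, Aim 1, except the recruitment number, which is from protocol section 10.

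- Recruited (protocol): 120
- Enrolled (SAP): 134; evaluable: 120; attrition: 10%
- OSA prevalence: 50%
- FACIT-F means: 36 without OSA and 30 with OSA, a difference of 6; SD 12 in both groups
- Two-sided two-sample t-test, alpha 0.05; stated power approximately 80%

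**Step 1. Reproduce the SAP's enrolment figure.** Enrolled = evaluable / (1 − attrition) = 120 / 0.9 = 133.3, rounded up to 134. Check: 134 × 0.9 = 120.6. The SAP figure reproduces exactly, so it is a deliberate calculation and contains no arithmetic error.

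**Step 2. Gap between the documents.** 134 − 120 = 14 people.

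**Step 3. Evaluable number if 120 is the intake.** 120 × 0.9 = 108, which is 12 fewer than the SAP assumes. At 50% prevalence that is 54 with OSA and 54 without.

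**Step 4. Aim 1 power.** Standardised difference d = 6/12 = 0.5. Noncentrality = d × √(n/2), with n per group and 2n − 2 degrees of freedom.

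| Case | n per group | Noncentrality | Power (t-test) | Power (normal approx.) | Difference detectable at 80% power (t-test) |
|---|---|---|---|---|---|
| 134 enrolled, 120 evaluable | 60 | 0.5 × √30 = 2.74 | 77.5% | 78.2% | 6.19 points |
| 120 enrolled, 108 evaluable | 54 | 0.5 × √27 = 2.60 | 73.1% | 73.8% | 6.53 points |

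The conditional loss by t-test is 77.53 − 73.06 = 4.5 percentage points. The remaining gap up to the SAP's stated approximate 80% is already there at 60 per group and is not caused by this inconsistency.

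**Step 5. Does other text settle the meaning of 120?** Section 26 expects 60 diagnoses. That is 50% of 120, whereas 50% of 134 would be 67. The figure therefore fits a base of 120, but it fits 120 recruited as well as 120 evaluable and does not decide the matter. The SAP's Aim 2 text speaks of 120 studied, which agrees with its own evaluable number.

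**The case against.** The strongest reply is that section 10 plainly means the evaluable number. The SAP is the only text that separates enrolled from evaluable, and it is explicit. Section 10 gives a bare parenthetical figure and does not call it a limit or maximum. Its sentence is also a loose summary: it sends all 120 to the research sleep study and PAP trial, although section 9 ends participation for those without OSA. Most of this stands. The evaluable reading is the more likely one, and under it the loss is zero. What survives is that section 10 says recruited, and nothing in the available text connects its 120 to the SAP's 134.

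Two stronger readings are tempting, and the documents do not support them.

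- A reader might infer that the plan leaves the enrolment target open. It does not: the SAP names 134. The defect is that section 10 does not match it.
- A reader might infer that the protocol, being later, replaced 134 with 120. The SAP is dated October 5, 2018, and protocol section 9 contains alternatives "in order to maintain social distancing and perform study activities remotely due to COVID-19". But section 9 describes those alternatives as additions under each visit, and section 8 still treats the protocol as an initial submission. The COVID-19 text dates those insertions. It does not show that section 10 was reconsidered after the SAP.

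The looseness over who has the research sleep study and PAP trial is a drafting matter that section 9 already settles. It is not part of this point.

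**Conclusion.** The mismatch is real: 120 recruited in the protocol, 134 enrolled for 120 evaluable in the SAP, a difference of 14, with no reconciling text among the pages available. Confidence in the mismatch is high.

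Any consequence for power is conditional. If section 10 quotes the evaluable number, which is probable, nothing is lost. If 120 were applied as the recruitment number, about 108 would be evaluable and Aim 1 power would be about 73% rather than 77.5%. This rests on the SAP's 10% attrition, 50% prevalence, 6-point difference and SD of 12. The expected OSA group would be 54 rather than 60, but only at exactly 50% prevalence; the SAP itself expects at least 60. It would go too far to say that this inconsistency leaves the trial underpowered.

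The correction should be made because enrolment size is a figure the trial relies on and the change is small.

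**What to change.** Amend protocol section 10 to state that 134 people will be enrolled to obtain 120 evaluable, matching the SAP. If 134 is already the working target, the cost is a one-line amendment.

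If recruitment has in practice been planned to stop at 120 and 134 is now adopted, the cost is 14 more participants through Aim 1 testing, an overnight sleep study and a blood draw. Section 20 sets the payment for completing only Aim 1 at $200, so added Aim 1 compensation is up to 14 × $200 = $2,800, plus Aim 2 and Aim 3 costs for those found to have OSA.

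Only if the sponsor confirms that 120 is the actual enrolment ceiling should the SAP be changed instead, to about 108 evaluable and about 73% power for Aim 1. That adds no participants but lowers the stated power. Restating the SAP's approximate 80% at 60 per group is a separate matter and is not needed for this correction.
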